5.3 Efficacy Assessment

5.3.1 CT/MRI and Bone Scan

Imaging including abdominopelvic CT/MRI, chest CT (if screening chest x-ray leads to diagnosis of thoracic metastasis), and Technicium-99m (Tc-99m) bone scintiography will be performed at the Screening Visit and assessed at Week 9, Week 17, Week 25 and at subsequent 12 week intervals. For subjects that discontinue for reasons other than radiographic progression or initiation of a new anti-neoplastic therapy, the imaging will be conducted every 12 weeks until progression, initiation of new anti-neoplastic therapy, loss to follow-up or death. Imaging performed prior to informed consent may be used as baseline so long as it is performed within the Screening period (days -28 to -1).

Scans should be scheduled in such a way that the scan results are available at the regularly scheduled visit.

The imaging method utilized for baseline scans must be utilized throughout the entire study.

Imaging may be performed at any time to confirm suspected progression of disease.

Radiographic evaluation of metastatic disease is determined separately for soft tissue and bone disease. Radiographic disease assessment for soft tissue disease is based on CT or MRI scan and is defined by RECIST 1.1. Radiographic disease assessment for bone lesions is based on bone scan and progression is considered when a minimum of two new lesions compared to baseline are observed.

Progression on bone scan at time points prior to or at Week 9 require a confirmatory scan performed six or more weeks later. This confirmatory scan should demonstrate at least 2 additional new lesions compared to the Week 9 scan (PCWG2).

Assessment will include tumor measurements for target lesions, non-target lesions, and assessment for any new lesions. An overall assessment will be characterized for that time point evaluation. At the end of study for that subject, the overall best response to the study regimen will be characterized.

Images (abdominopelvic [lung when applicable] CT/MRI and bone scan) should be read on site. Each site should ideally designate the same reader who will evaluate the images for any one subject for the duration of the study.

The same imaging method used for an individual patient at baseline should be used throughout the entire study for that patient.

PET scans should not be used to determine disease progression.

5.3.2 **PSA**

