7.4.2 Analysis of Secondary Endpoints

The overall survival rate at 1 year will be estimated via Kaplan-Meier methodology with censoring defined by the time of last contact with the subject for those subjects who do not have a reported death. This analysis will be repeated in each subset defined by prior treatment with exposure.

For patients with PSA declines, the PSA progression date is defined as the date that a $\geq 25\%$ increase and an absolute increase of $\geq 2~\mu g/L$ (2 ng/mL) above the nadir is documented, which is confirmed by a second consecutive value obtained 3 or more weeks later. For patients with no PSA declines, the PSA progression date is defined as the date that a $\geq 25\%$ increase and an absolute increase of $\geq 2~\mu g/L$ (2 ng/mL) above the baseline is documented, which is confirmed by a second consecutive value 3 or more weeks later. The time to PSA progression will then be estimated via Kaplan-Meier methodology with censoring defined by the time of the last available PSA measure. This analysis will be repeated in each subset defined by prior treatment with exposure.

The proportion of subjects achieving a maximum PSA decline from baseline of at least 30% (PSA30), 50% (PSA50), and 90% (PSA90), respectively, and having an objective response will provided along with 90% confidence intervals. Analyses for PSA response rates will include all subjects with at least one post-baseline PSA measure. Analysis for objective response will include all subjects with measurable disease at baseline. These analyses will be repeated in each subset defined by prior treatment with exposure.

The time to first use of a subsequent antineoplastic therapy will be estimated via Kaplan-Meier methodology with censoring defined by the time of last contact with the subject for those subjects who do not have a reported use of antineoplastic therapy. This analysis will be repeated in each subset defined by prior treatment with exposure.

The analysis described in Section 7.4.1.3 will be repeated for secondary endpoints as appropriate.

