Objective Response Rate (ORR) is the proportion of patients whose best overall response is Complete Response (CR) or Partial Response (PR) per RECIST 1.1. Only patients with measurable disease at baseline will be included in the analysis of ORR.

Best Overall Response is derived based on the time point response information on the CRF according to RECIST criteria for both subjects with measureable and non-measureable disease:

- CR
- PRNon Cr/Non Pd
- SD
- NE

The derivation of BOR is implemented using SAS based solely on investigator assessed information across all timepoints. Confirmation of response is not required according to the protocol.

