7 STATISTICAL METHODOLOGY

7.1 General Considerations

For continuous variables, descriptive statistics will include the number of subjects (n), mean, standard deviation, median, minimum and maximum. When needed, the use of other percentiles (e.g., 10%, 25%, 75% and 90%) will be mentioned in the relevant section.

Frequencies and percentages will be displayed for categorical data. Percentages by categories will be based on the number of subjects with no missing data, i.e., will add up to 100%.

All data processing, summarization, and analyses will be performed using SAS® Version 9.1.3 or higher on Unix. Specifications for table, figures, and data listing formats can be found in the TLF specifications for this study.

For the definition of subgroups of interest please refer to Section 7.8

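### The planned objective response rate counts single-scan, site-read responses without confirmation; it should be labelled unconfirmed and reported beside a confirmed rate

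*SAP*

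**What the plan says.** SAP 6.1.2 defines the endpoint: "Objective Response Rate (ORR) is the proportion of patients whose best overall response is Complete Response (CR) or Partial Response (PR) per RECIST 1.1". On the source data it says "Best Overall Response is derived based on the time point response information on the CRF according to RECIST criteria", and it specifies that the derivation uses only investigator-assessed information over all time points. It then states: "Confirmation of response is not required according to the protocol".

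The two documents agree on the denominator. SAP 6.1.2: "Only patients with measurable disease at baseline will be included in the analysis of ORR". Protocol 7.4.2: "Analysis for objective response will include all subjects with measurable disease at baseline". SAP 7.4.2 adds an exact (Clopper-Pearson) 90% confidence interval. No reference rate, threshold or test is attached to the overall ORR.

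On response itself, Protocol 5.3.1 says only "At the end of study for that subject, the overall best response to the study regimen will be characterized", and it refers to RECIST 1.1 for soft tissue. The same section has scans read on site at Weeks 9, 17 and 25 and every 12 weeks after that. The protocol's efficacy confirmation rules concern progression: bone progression at or before Week 9 (5.3.1) and PSA progression (7.4.2). Section 5.3.1 also allows extra imaging to confirm suspected progression.

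**The concern.** Taking the best of several time points without confirmation favours the most favourable reading. A patient whose lesions hover short of the response threshold gets a new chance to cross it at each scan, through measurement or reader variation, and one crossing is enough. The readers are the sites, who know the treatment, and there is no control arm in which the same upward pull would appear and cancel. The rate will be read in absolute terms.

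The treatment of confirmation is also uneven: early bone progression and PSA progression must be confirmed, and response need not be. Objective response is used again in SAP 7.4.3, where AR-V7 status and the AR-V7/V12 composite are each tested against it by Fisher's exact test. Any spurious responders would add misclassification there.

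Finally, the SAP sentence may lead a reader to think that the protocol considered and settled the matter.

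**Working it through.** **1. Is there a protocol rule?** The protocol names objective response as an objective and endpoint (2.1, 2.3.2), says that best response will be characterized (5.3.1), cites RECIST 1.1 (2.2.1, 5.3.1), and sets the analysis population and 90% interval (7.4.2). None of these sections addresses confirmation of response in either direction. RECIST 1.1 is cited but not reproduced, so what it would require here cannot be settled from the documents.

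**2. Is there a figure to reproduce?** Not for ORR. No expected rate, number of measurable patients or precision target is given. The counts below are therefore assumed.

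**3. Direction.** Every confirmed responder is also an unconfirmed responder, and the denominator is the same. So unconfirmed ORR is at least as large as confirmed ORR.

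**4. Size.** With n measurable patients and k unconfirmed responders, the difference is k/n.

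| n (assumed) | k = 1 | k = 3 |
|---|---|---|
| 40 | 2.5 points | 7.5 points |
| 20 | 5.0 points | 15.0 points |
| 16 | 6.3 points | 18.8 points |

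Example at n = 20, with 4 responders of whom 2 are unconfirmed:
- As planned: 4/20 = 20%, exact 90% CI 7.1 to 40.1%.
- Confirmed: 2/20 = 10%, exact 90% CI 1.8 to 28.3%.

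**5. How readily could one scan mislead?** This is a per-patient illustration with no inputs from the documents. Assume a response threshold of a 30% reduction, a constant true change μ, and an error SD σ of 8 to 12 percentage points. Then p = Φ((−0.30 − μ)/σ). With three independent scans:
- P(at least one crossing) = 1 − (1 − p)³
- P(two consecutive crossings) = p² + (1 − p)p²

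| μ | σ | p | At least one of 3 | Two consecutive |
|---|---|---|---|---|
| −15% | 8 | 0.0304 | 8.8% | 0.2% |
| −15% | 12 | 0.1057 | 28.5% | 2.1% |
| −10% | 8 | 0.0062 | 1.9% | 0.01% |
| −10% | 12 | 0.0478 | 13.7% | 0.4% |

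Independence is too favourable to the contrast, because all percent changes share one baseline measurement. With an assumed correlation of 0.5 and μ = −15%, the ranges over σ become:
- Three scans: 8 to 23% (at least one) against 1 to 5% (two consecutive).
- Two scans: 5 to 18% (at least one) against 0.6 to 3.5% (both).

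Three scans is itself optimistic. On the plan's exponential model with a 4-month median (SAP 4), the proportion progression-free is 0.5^(3.68/4) = 53% at Week 17 and 0.5^(5.52/4) = 38% at Week 25, ignoring losses.

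**6. Does the best-response list matter to ORR?** As it reads here, the list has CR, the run-together entry "PRNon Cr/Non Pd", SD and NE, with no separate PD. The numerator is CR or PR, and the denominator is measurable disease at baseline. Neither uses the PD label. With 2 responders among 20, ORR is 2/20 = 10% with or without a PD entry.

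**The case against.** **The SAP sentence is true as written.** If it means that the protocol imposes no requirement, it is correct. A reader might infer that the SAP invokes a non-existent rule or contradicts the protocol. The documents do not support that: the protocol is silent, and the SAP pre-specifies how it resolves the silence. This objection stands. What remains is that the wording lets an analysis choice look like a protocol provision.

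**The missing PD entry does not inflate ORR.** A reader might combine the list with SAP 7.1, "Percentages by categories will be based on the number of subjects with no missing data, i.e., will add up to 100" percent, and infer that patients with progression only would drop out of the denominator. That would require coding a recorded progression as missing data and overriding the measurable-disease denominator that both documents state. The SAP does not say this will be done. The list is also visibly damaged at this point, so a PD line may have been lost in reading the PDF. This objection stands in full.

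**The per-patient probabilities are not a trial effect.** They apply to hypothetical patients with a fixed shrinkage, and independence and three scans per patient overstate the contrast. This stands. They show a mechanism, and the gap stays several-fold under the less favourable assumptions above, but they do not predict this trial's ORR.

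**A confirmed rate has its own bias.** Scheduled imaging stops at radiographic progression or new anti-neoplastic therapy (Protocol 5.3.1, 6.1). A real response with no later scan would count as unconfirmed. This also stands. It is a reason to show both rates rather than replace one with the other.

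**Conclusion.** The point holds as a modest one. SAP 6.1.2 counts single-time-point responses, the protocol does not address confirmation, and the resulting ORR can only equal or exceed a confirmed rate. The difference is k/n: 2.5 to 18.8 points for 1 to 3 unconfirmed responders among 16 to 40 measurable patients, all assumed counts. The documents give no basis for saying how many unconfirmed responders there will be.

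No type I error or go/no-go rule is affected. What is affected is the interpretation of a descriptive rate without a comparator and, secondarily, the biomarker comparisons that reuse it.

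The absence of PD from the list is a completeness check only, with an effect of 0 points on ORR under the stated denominator.

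**What to change.** In SAP 6.1.2:

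1. Replace the attribution with a statement that the protocol does not address confirmation of response and that the SAP's planned rate does not require it.
2. Label that rate unconfirmed ORR.
3. Report beside it a confirmed ORR, defined as CR or PR maintained at the next scheduled scan. Give each rate its exact 90% interval over all subjects with measurable disease at baseline.
4. State that a responder with no later scan counts as unconfirmed, and report how many there are.
5. Check the best-response list against the original, and add PD if it is absent. A sentence saying that PD, NE and missing best response count as non-responders would prevent any misreading of the general percentage rule in SAP 7.1.

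The cost is SAP wording and one more derived variable. No extra scans are needed, since the scheduled assessments are nominally 8 weeks apart up to Week 25 and 12 weeks apart after that. The confirmed rate will be equal or lower, and it will understate response where imaging stopped early, so neither rate should stand alone.

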6.1.3 Exploratory Efficacy Endpoints

Samples were collected serially at baseline, week 13, at time of PSA progression, and time of radiographic progression and analyzed at central labs for:

- 1) Androgen receptor
 - a. AR-V7
 - b. AR-FL
 - c. AR-V7/AR-FL ratio
- 2) Glucocorticoid receptor
 - a. GR-FL
- 3) AR mutations;
 - a. L702H
 - b. W741C
 - c. F876L
 - d. T877A
- 4) Circulating tumor cell detected
- 5) Inflammatory biomarkers
 - a. IL6
 - b. IL8
 - c. TNF- α (tumor necrotic factor alpha)
 - d. sTNFR1 (soluble TNF receptor-1)
- 6) Neuroendocrine biomarkers
 - a. CgA (chromogranin A)
 - b. NSE (neuron specific enolase)
 - c. Synaptophysin

Other biomarkers may be identified for analysis and SAP will be amended accordingly prior to database lock.

6.1.4 Other Efficacy Variables

A composite endpoint of time to composite progression free survival (cPFS), defined as the earliest date of either radiologic progression, clinical progression, or death, will be analyzed. Radiologic events will be defined as described in Section 6.1.1. Date of clinical progression is the earliest onset date of any AE determined by investigator to be clinical progression.

cPFS will be censored in the following scenarios:

- If patient has no composite PD event the cPFS will be censored at last visit date.
- If patient took any new systemic anti-cancer therapy before any composite PD event, the cPFS will be censored at the last visit date prior to the date of new anti-cancer therapy.

6.2 Safety Variables

Safety will be assessed by evaluation of the following variables:

- Treatment-emergent adverse events (TEAEs; frequency, severity, seriousness, and relationship to study drug).
- Clinical laboratory variables (hematology, biochemistry including liver enzymes and total bilirubin, and urinalysis)
- Vital signs (systolic and diastolic blood pressure and pulse rate)
- ECOG PS

TEAE is defined as an adverse event observed after first dose of study medication. All adverse events collected that begin within 7 days after taking the last dose of study drug will also be counted as TEAE. Any AE with missing onset date will be considered as TEAE, unless the year and month are prior to the first dose of study medication.

A drug-related TEAE is defined as any TEAE with at least possible relationship to study treatment as assessed by the investigator or with missing assessment of the causal relationship.

Serious adverse events (SAEs) include adverse events that are flagged as serious by the investigator on eCRF, or upgraded by the Sponsor based on review of the Sponsor's list of Always Serious term.

The adverse events will be coded by body system using a MedDRA® dictionary. The severity of adverse event will be graded by NCI CTCAE Grade.

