5.4.2 Adverse Events

AE collection will begin from the time of informed consent and continue through 30 days after last dose. See **Section 5.5 Adverse Events and Other Safety Aspects** for information regarding adverse event collection and data handling.

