5.5.8 Follow-up of Adverse Events

All AEs occurring during or after the subject has discontinued the study are to be followed up until resolved or judged to be no longer clinically significant, or until they become chronic to the extent that they can be fully characterized.

If during AE follow-up, the adverse event progresses to an "SAE", or if a subject experiences a new SAE, the investigator must immediately report the information to the Sponsor.

Please refer to **Appendix** 12.2 Liver Safety Monitoring and Assessment for detailed instructions on Drug Induced Liver Injury (DILI).

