7.5.2 Clinical Laboratory Evaluation

Quantitative clinical laboratory variables, i.e., hematology, biochemistry, and urinalysis will be summarized using mean, standard deviation, minimum, maximum and median at each visit. Additionally, a within-subject change will be calculated as the post-baseline measurement minus the baseline measurement and summarized in the same way. Baseline is defined as the last available measurement prior to the first study drug dose.

Frequency tabulations of qualitative clinical laboratory variables (urinalysis) will be presented at each visit.

Laboratory results will also be graded using NCI-CTCAE, where possible. Parameters that have criteria available for both low and high values, i.e., hypo- and hyper-, will be summarized for both criteria. The same subject can be counted for both values if the subject has different laboratory values meeting each criterion. NCI-CTCAE grade of laboratory evaluations will be summarized by number and percentage of subjects for each visit. Shift

tables of lab parameters NCI-CTCAE grade change from baseline to worst post-baseline grade will also be presented.

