7.11.1 Missing Data

As a general principle, no imputation of missing data for other variables will be done. Exceptions are the start and stop dates of AEs and concomitant medication. If day is missing from any date in a derivation then calculate the derived value using 15th day of month. If month or year is missing from any date in a derivation then set the derived value to missing.

Adverse events with missing relationship will be summarized as 'Related to Study Drug'. Adverse events with missing severity grade will be handled as 'missing'.

Incomplete onset dates default AEs to treatment emergent. Listings of the AEs and concomitant medications will present the actual partial dates; imputed dates will not be shown.

Cases where the onset date of an AE is (partially) missing, will be addressed prior to or during the DRM in order to determine whether the AE must be considered treatment emergent or not.

Imputation on missing date of initial diagnosis (cancer duration) and cancer treatment history (start date, stop date, or date of procedure) will be done as follows:

- Incomplete Day: use the 15th day of the month
- Incomplete Month: use 1st of July if the Year is before Year of dosing, otherwise missing.
- Incomplete Year: no imputation, the derived variable is considered to be missing.

Imputation methods will not be used to determine other endpoints.

Listings will always show the original date information without imputation, but derived parameters (TEAE indicator, start day, end day, study day) will be flagged.

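### The SAP's treatment-emergent definition has no worsening clause, so an adverse event that starts in screening and worsens on enzalutamide can be left out of the TEAE tables

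*SAP*

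**What the plan says.** SAP 6.2 defines the term in one sentence: "TEAE is defined as an adverse event observed after first dose of study medication". Two rules follow. One covers the end of treatment: "All adverse events collected that begin within 7 days after taking the last dose of study drug will also be counted as TEAE". The other covers missing dates: "Any AE with missing onset date will be considered as TEAE, unless the year and month are prior to the first dose". SAP 7.11.1 repeats the default: "Incomplete onset dates default AEs to treatment emergent". None of these mentions a change in grade or seriousness.

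Collection starts before dosing. Protocol 5.4.2 states: "AE collection will begin from the time of informed consent and continue through 30 days after last dose". The length of screening is given in the study schedule and in Protocol 5.3.1, which allows baseline imaging if "performed within the Screening period (days -28 to -1").

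SAP 7.5.1 builds its adverse event summaries on TEAEs: overall, by CTCAE grade, serious, drug-related, leading to permanent discontinuation, common, and of special interest. The only item not restricted to TEAEs is the number of deaths.

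For laboratory data, SAP 7.5.2 does measure worsening. It plans shift tables of "lab parameters NCI-CTCAE grade change from baseline to worst post-baseline grade".

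**The concern.** A definition that looks only at onset asks whether the event was new after the first dose. It does not ask whether the event got worse after the first dose. Worsening on drug is also a safety signal.

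Safety of re-treatment is a secondary objective, and the trial has one arm, so there is no control group in which the same omission would show up. Fatigue, falls and neutropenia are on the SAP's special-interest list. Each could begin in the weeks between consent and Day 1 and then become more severe or serious on drug. If that history sits in one record dated before Day 1, the serious, by-grade and special-interest tables would not show it.

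**Working it through.** The plan states no figure to reproduce here. The check is a reading of the rules, followed by simple arithmetic on table rows.

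**Step 1: which date decides?** The word *observed* in the first sentence of SAP 6.2 is loose. The next two sentences turn on when the event begins and on its onset date, and SAP 7.11.1 also speaks of onset dates. Read together, the rule is one of onset after the first dose.

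**Step 2: is worsening covered elsewhere?** Treatment-emergent status is also addressed in Protocol 7.9 (date imputation), SAP 7.11.1 (missing dates) and SAP 7.5.1 (the tables). None has a worsening clause. SAP 7.5.1 does take the worst grade per subject, but only among records already classed as TEAEs, so it cannot bring in a record excluded by its onset.

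**Step 3: a hypothetical case.** Fatigue starts on Day -10 at grade 1 and reaches grade 3 during treatment.

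| Recording practice | Onset on the record | TEAE under SAP 6.2? | In the SAP 7.5.1 TEAE tables? |
|---|---|---|---|
| One record kept, grade updated | Day -10 | No | No |
| New record opened at the increase | Date of the increase | Yes | Yes, at grade 3 |

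Protocol 8.1.5 leaves eCRF completion to separate instructions. Neither document says which row of this table applies.

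**Step 4: what one subject is worth.** Inputs: 40 subjects planned (Protocol 2.2.1, SAP 3.2); common-TEAE threshold 5.0% (SAP 7.5.1); all 40 assumed dosed and so in the safety analysis set.

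- One subject: 1/40 = 2.5%, below the threshold.
- Two subjects: 2/40 = 5.0%, which meets it.

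One misclassified subject therefore moves a row by 2.5 percentage points and can decide whether a preferred term enters the common-TEAE table.

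**Step 5: how many subjects?** This needs the share with an event starting between consent and Day 1, and the share of those that worsen. The documents give neither, so no count is offered.

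**The case against.** The strongest objection is that the loss is conditional. If the eCRF instructions require a new record when the grade rises, the worsening is captured. SAP 7.5.1 allows for one subject having several TEAEs of the same term at different severities, which fits that practice. Protocol 5.4.4 also has clinically relevant adverse changes on physical examination recorded as adverse events. This stands: the text leaves a risk open and does not establish a loss. It does not close the gap, because the SAP neither states nor cites such a recording rule.

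The affected group is also narrow. Protocol 5.2.2 puts past and present conditions at screening into the medical history. A reader might infer that residual taxane toxicity in general falls through the definition. The documents do not support that: the gap concerns events that newly start between consent and Day 1.

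A reader might also infer that a worsened event would survive only in listings. That goes too far. Protocol 7.5.1 plans summaries of adverse events, serious events, related events and discontinuations without the treatment-emergent restriction. SAP 7.2.1 and 7.3.1 count reasons for discontinuation, dose reductions and interruptions. Laboratory-based worsening, including neutropenia, appears in the shift tables. The omission is from the SAP 7.5.1 TEAE tables.

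Taken literally, *observed after first dose* might suggest the opposite error, with unchanged screening events counted as emergent. The onset-based sentences around it contradict that, and SAP 6.2 expressly excludes a partial date whose year and month precede the first dose.

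Finally, Protocol 5.5.8 might be read as expecting screening events to progress. Its wording, "during AE follow-up, the adverse event progresses to an" SAE, opens with *if* and sets a duty to report to the sponsor. It predicts nothing and does not say how a grade change is recorded.

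**Conclusion.** The gap is real and modest. SAP 6.2 classifies by onset and has no worsening clause. An event that starts between consent and Day 1 and then rises in CTCAE grade or becomes serious on enzalutamide is left out of the TEAE tables by grade, seriousness, relatedness, discontinuation and special interest. This rests on one assumption that the documents cannot settle: that the event stays one record with its pre-dose onset date.

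The effect falls on individual preferred-term, grade and seriousness rows, at 2.5 percentage points per subject. The row for any TEAE should barely move, since Protocol 1.3 reports that nearly all treated patients in earlier studies had at least one adverse event. rPFS, the sample size and the laboratory shift tables are unaffected. The definition should be corrected before database hard lock because, as written, it can produce a wrong safety count.

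**What to change.** Replace the definition in SAP 6.2 with wording such as:

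> A TEAE is an adverse event with onset on or after the first dose and through 7 days after the last dose, or an adverse event with onset before the first dose whose CTCAE grade or seriousness increases on or after the first dose within the same window. A screening adverse event that does not increase is not a TEAE.

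Then confirm in the eCRF instructions that such an increase is recorded with its date, whether as a new record or as a dated grade change. Query any pre-dose-onset records already entered. SAP 6.1.3 describes the biomarker samples in the past tense, so data collection may be well advanced and a note to sites alone would not repair existing records.

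The cost is one revised definition, one check of the eCRF instructions and a few queries. TEAE counts may rise slightly. SAP section 1 allows version-controlled revisions before hard lock. No dosing or clinical rule changes.
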